APPENDIX G: Drug Diary85

1. SUMMARY

Excess body weight is a significant risk factor for many cancers, especially breast cancer. Obesity can affect survivorship and quality-of-life factors including sexual function, neuropathy, cardiotoxicity, chronic fatigue and lymphedema. In retrospective studies, patients with a history of or current breast cancer who are overweight or obese are at an increased risk of therapy-related morbidity, recurrence, and breast cancer-related mortality^{1,2}. Most cancer guidelines recommend that breast cancer survivors who are overweight or obese lose weight and that those within a normal body mass index (BMI) maintain a stable body weight. The cornerstone of interventions to treat or prevent obesity includes lifestyle modification with diet and exercise; however, integration into clinical practice is challenging due to limitations with standardization and scalability.

Our collaborators from the Welch Center for Prevention, Epidemiology, and Clinical Research at the Johns Hopkins University have reported impressive and sustained weight loss in randomized controlled trials designated Practice-based Opportunities for Weight Reduction (POWER) in obese women with at least one cardiovascular risk factor using a remote-support weight loss intervention³. This remote-support weight loss intervention of the POWER study has been adapted in women with early breast cancer who are overweight or obese, designated POWER-remote, and demonstrated statistically significant weight loss of $\geq 5\%$ body weight, compared to self-directed weight loss at 6 and 12 months⁴. Our recent evaluation of 6 months of the POWER intervention in breast cancer survivors found that 46% of women randomized to the POWER-remote arm were able to lose $\geq 5\%$ of their baseline weight as compared to only 10.9% of women in the self-directed arm.

While some patients with early stage breast cancer are able to achieve significant clinically meaningful loss, the majority are unable to. The goal of this project is to evaluate whether weight loss in overweight/obese breast cancer survivors whose trajectory suggests unlikelihood of attaining clinically significant weight loss of ≥5% with behavioral intervention alone can be augmented with pharmacotherapy. Studies have shown that self-directed weight loss is generally not successful. Our POWER-remote study showed that 89.1% of women in the self-directed arm were not successful in weight loss. With the implementation of remote behavioral intervention, this value drops to 54% of women not being able to lose at least 5% of their weight. We will focus on this population of women, as they may be identified earlier (after 4-12 weeks of behavioral intervention). Success for this study will be measured by the rate of these women who are able to achieve weight loss with the adapted behavioral intervention with pharmacotherapy. As there are over 3 million breast cancer survivors in the US⁵, many of whom are overweight/obese, underutilization of anti-obesity drugs may be a critical and neglected component of weight loss treatment.

We will evaluate the extent to which implementation of a chronic weight loss medication, Contrave® (Naltrexone/Bupropion), is associated with achieving \geq 5% weight loss. All patients will receive the POWER-remote behavioral weight loss intervention (BWL) and have a behavioral coach for the duration of the 6 month study. During months 1-3, the behavioral coach will call weekly. From months 4-6, the behavioral coach will call monthly. At week 9, those who lose \geq 5%, designated fast responders, will continue with BWL alone (FAST-BWL) while those

[figure not shown]
who lose <5%, designated slow responders, will continue BWL and initiate Contrave (SLOW-BWL). The SLOW-BWL arm will receive at least 16 weeks of Contrave (as per Federal Drug Administration [FDA] recommended administration) starting at week 9 and discontinue if ≥5% weight loss is not achieved at month 6. During month 3, all participants continue to have weekly calls with the behavioral coach and will be asked about symptoms, which may be related to initiation of pharmacotherapy; any symptoms are reported to the Protocol Chair for further evaluation. In addition to total weight loss, we will evaluate biomarkers associated with obesity, microbiome and cardiometabolic factors.

The ability of a diet and behavioral interventions to promote a more favorable microbiome profile, a lower BMI, and reduced levels of inflammatory cytokines, may help explain why vegetarian diets, and particularly vegan diets, seem to be protective against cancer growth in general and PC in particular. Our study, through its focus on inflammatory biomarkers, analysis of fecal microbiota, and traditional metabolic endpoints such as weight loss, adiposity, insulin resistance and hyperlipidemia, will help elucidate the complex interplay between metabolic disorders and inflammation in breast cancer survivors. Perhaps more importantly, we are confident that our study will offer breast cancer survivors a low-risk strategy to weight management, with tremendous potential for near-term impact on their quality of life and health outcomes. We will also assess certain genotypes to determine whether the effect of an adaptive weight loss intervention on biomarkers is greater in the patients who have a particular genotype (e.g. AA-SOD2). The potential increase in antioxidants in the adaptive weight loss intervention may enable certain patients with certain genotypes to gain greater benefit from the diet than others.

Our research will address a major gap in the literature that could potentially improve quality of life and cancer and non-cancer outcomes for obese breast cancer patients. While many studies have explored various interventions for weight loss in cancer survivors, to our knowledge none have explored the influence of weight loss pharmacotherapy in breast cancer survivors. Additionally, these medications have not been studied in the setting of use of hormonal therapy, such as tamoxifen or an aromatase inhibitor. The data will be used not only to assess the impact of weight loss and biomarker modulation but also to design definitive studies available to all overweight and obese women with breast cancer whom struggle to achieve clinically significant weight loss despite lifestyle intervention.

2. SCHEMA

FIGURE 1: Study design for Adaptive Nutrition & Exercise Weight Loss Study with pharmacotherapy

3. HYPOTHESIS

- In SLOW-BWL, adding Contrave at week 9 of a weight loss intervention may augment BWL and allow women to lose \geq 5% of their baseline body weight at 6 months.
- In SLOW-BWL, weight loss of $\geq 5\%$ baseline body weight will be associated with changes in the following from baseline to 2 and 6 months:
 - o reductions in fasting glucose, fasting insulin, total and low-density lipoprotein (LDL) cholesterol, triglycerides, leptin;
 - o increases in high-density lipoprotein (HDL) cholesterol and adiponectin;
 - o altered gut microbiome (decrease in the ratio of bacteroides and firmacutes); and
 - o improved patient reported outcomes (PROs)
 - o increased total lean mass, and decreased % fat mass and visceral fat
- Compared to women who are able to achieve at least 5% weight loss with 2 months of behavioral intervention alone, women who are unable to achieve ≥5% weight loss with behavioral intervention alone may have identifiable baseline characteristics (i.e., cardiometabolic profile, obesity biomarker, microbiome composition or PROs) that may be predictors of whom may benefit from earlier initiation of pharmacotherapy.

4. OBJECTIVES

4.1 Primary Objectives

4.1.1 To assess the rate of SLOW-BWL patients attaining at least 5% weight loss of their baseline body weight at 6 months with the addition of Contrave to BWL at week 9.

4.2 Secondary Objectives

- 4.2.1 To compare cardiometabolic biomarkers (HbA1c, IGF 1, fasting glucose, fasting lipids, fasting insulin, adiponectin and leptin levels), microbiome composition, body composition, and PROs at 2 and 6 months to baseline levels among SLOW-BWL who achieve ≥5% weight loss.
- 4.2.2 To compare cardiometabolic biomarkers, microbiome composition, body composition, and PROs at baseline of SLOW-BWL women who achieve ≥5% weight loss versus the SLOW-BWL women who do not achieve 5% weight loss.
- 4.2.3 To compare the moderate to vigorous physical activity (MVPA) and daily steps at 2 and 6 months to baseline levels among SLOW-BWL who achieved ≥5% weight loss vs the SLOW-BWL who did not achieve 5% weight loss.

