5.10 Patient Reported Outcomes (PROs)

^{**}NB32 (Naltrexone SR 32 mg/day and Buproprion SR 360mg/day)

^{***} From week 28-44, nonresponders on NB32 were re-randomized to either continue NB32 or change to Naltrexone SR 48mg/day and Buproprion SR 360mg/day

Being overweight or obese has an important impact on patients' functioning and well-being, particularly physical function⁹⁹. Thus, it will be important to assess the impact of weight loss and POWER-remote on patient-reported outcomes, including pain, fatigue, mental well-being, physical function, endocrine symptoms, sleep, sexual function, and medication adherence. The original POWER study investigated PROs using the MOS SF-12 physical component summary and mental component summary, the EuroQoL-5 dimensions single index and visual analog scale, the Patient Health Questionnaire-8 (PHQ-8) depression symptoms, and the Pittsburgh Sleep Quality Index (PSQI) sleep quality scores at baseline and 6, 12 and 24 months. We will notify the primary oncology provider if the PHQ-8 score is ≥15 (moderately severe or severe depression).

Physical domains were most affected, especially in subjects who lost weight. In another study which involved postmenopausal women undergoing a dietary and/or exercise intervention, weight loss predicted improvement in self-reported physical function, vitality, and mental health ¹⁰⁰. Since physical function has most consistently been found to be improved by weight loss, it will be our primary PRO. Studies in cancer patients suggest a 4-6 point change in score in Physical Function using the National Institute of Health (NIH) Patient-Reported Outcome Measurement Information System (PROMIS) questionnaire to be clinically meaningful ¹⁰¹. Since minimally important differences is usually estimated by taking half the estimated standard deviation, and in conjunction with the aforementioned studies, we conservatively hypothesize that, compared to baseline, weight loss at 6 months will be associated with an increase of five points in PROMIS, as determined by version 1 short-form to assess physical function. This form was also used in the POWER-remote study.

We will also administer a questionnaire to evaluate modulation in other PROs including: pain, fatigue, mental well-being, sleep, endocrine symptoms, and sexual function. Participants will also complete a drug diary to monitor medication adherence.

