13. DATA ANALYSIS AND STATISTICAL CONSIDERATIONS

13.1 Study Design

This is a prospective, non-randomized clinical trial assessing the effects of the addition of pharmacotherapy to a behavioral weight loss intervention in overweight/obese breast cancer patients on an AI who are unable to attain at least 5% weight loss after 8 weeks of lifestyle intervention alone.

All enrolled patients will participate in a 6-month BWL program. At week 9, patients who achieve ≥5% weight loss from baseline will continue with BWL (FAST-BWL). Those failing to achieve a minimum of 5% weight loss will receive Contrave in addition to BWL (SLOW-BWL). After a 4-week titration of Contrave, SLOW-BWL will have their drug adherence logs and any new symptoms reviewed by the Protocol Chair and/or co-investigators. The participants will be prescribed the constant dose for 3 months until the end of study (drug will be shipped to patient's home).

The primary endpoint of this study is the proportion of SLOW-BWL patients who achieve at least 5% weight loss of their enrollment baseline weight at 6 months with the addition of Contrave to BWL. We anticipate 55% of 55 subjects enrolled will be in the SLOW-BWL group, resulting in a sample size of approximately 30 SLOW-BWL women and 25 FAST-BWL women.

The secondary endpoints include baseline, 2 and 6 months values in all participants for the following: cardiometabolic biomarkers (fasting glucose, fasting lipids, fasting insulin, adiponectin and leptin levels), genotypes, microbiome composition, body composition, patient-reported outcomes (PROs), and physical activities.

Simon's two-stage minimax design will be used for the SLOW-BWL group. The null hypothesis that the true rate of attaining $\geq 5\%$ weight loss is 10.9%, which is chosen based on the rate of

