women attaining \geq 5% weight loss in the self-directed arm in the POWER-remote study.⁴ In the first stage, 15 SLOW-BWL women will be accrued. If there is 1 or fewer woman out of the 15 women who attain \geq 5% weight loss of their baseline weight, the study will be stopped. Otherwise, 15 additional SLOW-BWL women will be accrued for a total of 30 SLOW-BWL patients. The study does not plan to hold enrollment or treatment for the interim analysis. The null hypothesis will be rejected if 7 or more women are observed in the 30 patients who attain \geq 5% weight loss. This design yields a power of 80% at type I error rate of 5% when the true rate of attaining \geq 5% weight loss of the baseline weight for the SLOW-BWL women is 29%, a clinical meaningful rate for the SLOW-BWL women group.

Our results will inform us of how to better treat obesity in this vulnerable group of breast cancer patients. It may allow us to develop larger adaptive trials to assess long term breast cancer and non-cancer outcomes of behavioral interventions that incorporate pharmacotherapy. Additionally, our results may shed light on other modulators or obesity, such as biomarkers and the microbiome, laying foundation to future trials investigating additional interventions in breast cancer survivors who struggle with weight loss.

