13.2 Analysis Plans

Data will be summarized using descriptive statistics (continuous data) and/or contingency tables (categorical data) for demographic and baseline characteristics, efficacy measurements at 2 and 6 months, and safety measurements throughout the study.

For the primary analysis, the study will be considered successful if there are 7 or more SLOW-BWL patients who could achieve more than 5% weight loss compared to their baseline weight, which implies that the success rate regarding to >=5% weight loss will be significantly higher than 10.9%.

Univariate analysis will be conducted to compare outcomes at different time points including baseline, 2 months and 6 months, and to compare outcomes from different groups including SLOW-BWL patients who attain ≥5% weight loss or <5% weight loss of their enrollment baseline weight at 6 months and FASE-BWL patients. Wilcoxon rank sum and Wilcoxon sign rank tests will be conducted when appropriate. Student's t-test will also be performed when the outcomes are normally distributed after necessary data transformation. Moreover, mixed effect regression analysis will be conducted to evaluate the longitudinal trend in the outcomes at different time points.

Furthermore, multivariate logistic regression analysis will be conducted to evaluate the effect of the baseline characteristics on attaining \geq 5% weight loss of the baseline weight at 2 months among FAST- and SLOW-BWL patients, and to evaluate the effect of the baseline characteristics and the weight loss at 2 months on attaining \geq 5% weight loss of the baseline weight at 6 months for SLOW-BWL patients.

The primary analysis dataset will be based on the intent-to-treat population. Analysis based on the per-protocol population will also be conducted as exploratory analysis. Missing data will be handled by multiple imputation and sensitivity analysis.

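### Objective 4.2.1 tests change only within SLOW-BWL responders (about 9 women), so on its own it cannot test the hypothesised association with weight loss, and Section 13.2 does not say which analysis does

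*Combined protocol and SAP*

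**What the plan says.** The second hypothesis in Section 3 is about association: among SLOW-BWL women, a loss of 5% or more goes with favourable changes in metabolic markers, microbiome, PROs and body composition from baseline to 2 and 6 months.

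The objectives that could address it are in Section 4.2:

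- **4.2.1** compares cardiometabolic markers, microbiome, body composition and PROs "at 2 and 6 months to baseline levels among SLOW-BWL who achieve" the 5% threshold. It has no comparison group.
- **4.2.2** compares responders with non-responders on the same measures, but at baseline only.
- **4.2.3** compares responders with non-responders over time, but only for physical activity and steps.

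Section 5.10 gives the only effect size for a secondary outcome. It expects that "weight loss at 6 months will be associated with an increase of five points in PROMIS", measured by the physical function short form.

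Section 13.2 is general. "Univariate analysis will be conducted to compare outcomes at different time points", and the same sentence adds comparisons between SLOW-BWL women above and below 5% at 6 months and FAST-BWL women. A mixed-effect regression is planned for the longitudinal trend. None of these is linked to a numbered objective. Section 13.1 has the secondary outcomes collected in all participants at all three visits.

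**The concern.** An association with weight loss needs women with different amounts of weight loss. Objective 4.2.1 keeps only those above a cut-off measured at 6 months and asks whether they changed. If leptin falls or physical function rises in them, the cause could be weight loss, the passage of time, six months of coaching, or Contrave acting by another route. The analysis offers no way to tell.

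The 2-month comparison adds little. By definition these women had lost less than 5% at week 9 and had not started Contrave, yet they are selected on a result reached four months later.

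The subset is also small, so a real change could easily be missed. An analyst who followed 4.2.1 literally would report a low-powered responder-only test as the answer to the Section 3 hypothesis.

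**Working it through.** **1. The plan's own power figure.** Inputs from Section 13.1: "In the first stage, 15 SLOW-BWL women will be accrued"; "If there is 1 or fewer woman out of the 15 women who attain" the threshold, the study stops; otherwise "15 additional SLOW-BWL women will be accrued for a total of 30 SLOW-BWL patients". The final rule is "The null hypothesis will be rejected if 7 or more women are observed in the 30 patients who attain" the threshold. The null rate is 10.9% and the alternative 29%.

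P(reject) = Σ over x = 2 to 15 of P(X₁ = x) × P(X₂ ≥ 7 − x), with X₁ and X₂ both binomial(15, p).

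- p = 0.29 gives 0.8006.
- p = 0.109 gives 0.0378.

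The stated 80% power and 5% type I error are reproduced. They concern the primary endpoint only; no power is stated for 4.2.1.

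**2. Number of women in 4.2.1.** "We anticipate 55% of 55 subjects enrolled will be in the SLOW-BWL group": 0.55 × 55 = 30.25, about 30. At 29%, 30 × 0.29 = 8.7 responders, with a 95% binomial range of 4 to 14. Seven is the success bound, not an expected count. At the null rate, 30 × 0.109 = 3.3. Section 9.1.1 allows missed blood samples, so biomarker counts can be lower.

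**3. Power of the before/after test.** Two-sided 5% paired t-test: noncentral t with n − 1 degrees of freedom and noncentrality d√n, where d is the mean change divided by the SD of change.

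| n | d = 0.5 | d = 0.8 | d = 1.0 | d detectable at 80% |
|---|---|---|---|---|
| 7 | 20% | 43% | 60% | 1.27 |
| 8 | 23% | 50% | 68% | 1.16 |
| 9 | 26% | 56% | 75% | 1.07 |

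A 0.5 SD change needs 34 women for 80% power. The signed-rank test, also planned, has a smallest two-sided p-value of 2/2ⁿ. With 5 responders that is 0.0625, so it could never reach 5%.

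**4. The 5-point PROMIS change.** Appendix F gives a score SD of 10, which is cross-sectional. The SD of change is not given. For an assumed baseline to follow-up correlation ρ it is 10√(2(1 − ρ)).

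| ρ (assumed) | SD of change | d = 5/SD | Power, n = 7 to 9 |
|---|---|---|---|
| 0.3 | 11.83 | 0.42 | 16% to 20% |
| 0.5 | 10.00 | 0.50 | 20% to 26% |
| 0.7 | 7.75 | 0.65 | 30% to 40% |
| 0.8 | 6.32 | 0.79 | 42% to 55% |
| 0.9 | 4.47 | 1.12 | 70% to 84% |

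**5. Adding the non-responders.** The split in Section 13.2 supplies the missing contrast but little power. Comparing 7 to 9 responders with 23 to 21 non-responders (two-sample t-test), a 0.5 SD difference in change has 20% to 23% power.

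Using percentage weight change as a continuous variable keeps information that the split discards. Simulation with n = 30, bivariate normal weight change and outcome change, 29% above the cut, two-sided 5% (figures good to about one percentage point):

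| Assumed correlation | Continuous weight change | Responder split |
|---|---|---|
| 0.2 | 19% | 13% |
| 0.3 | 37% | 23% |
| 0.4 | 62% | 38% |
| 0.5 | 83% | 55% |

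This is a simple slope test with complete data, used as a guide to the weight-change coefficient in the mixed model. Women without a 6-month weight would lower these figures.

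**The case against.** The strongest reply is that the plan already contains the contrast. Section 13.2 lists SLOW-BWL women above and below 5% among the groups to be compared and adds mixed models, and the data will exist for everyone. That stands. A reader might infer from 4.2.1 that the trial cannot show the hypothesised association at all; the documents do not support that. What remains is that Section 13.2 assigns no analysis to 4.2.1, describes its mixed model as one for trend over time, and does not say which result answers Section 3.

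A second reply is that low power in a secondary objective of a small single-arm phase II study is a limitation of size, and that no power was claimed. That also stands: no stated figure is wrong, and describing change in women who reached 5% is a legitimate descriptive aim.

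A third is that the count of 7 to 9 is not fixed. If the one-year response rates in Section 5.9 applied (44.5% to 66.4%, a different population and time point), about 13 to 20 women would qualify, and power for a 0.5 SD change would be 41% at 14 women and 57% at 20. The missing comparator would remain.

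Finally, a reader might infer that moving to all 30 women cures the power problem, since a paired test has 75% power for 0.5 SD and 99% for 0.8 SD at n = 30. Those figures are for a mean change in all women, not for an association with weight loss, and they assume that non-responders change as much as responders. If only responders changed by 0.5 SD, the overall mean would be 0.29 × 0.5 = 0.145 SD and power about 12%, holding the SD of change at 1. Such a test would also leave time, coaching and drug unseparated.

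**Conclusion.** The point holds as a mismatch between a hypothesis and the objective meant to serve it. Objective 4.2.1 alone cannot test the association in Section 3, and it rests on about 9 women with 20% to 26% power for a 0.5 SD change at n = 7 to 9. For the PROMIS target, power runs from about 16% to 84% over assumed correlations of 0.3 to 0.9, and it approaches or passes 80% only near 0.9.

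A better analysis is available from data already planned. Continuous weight change in all SLOW-BWL women is more powerful than the responder split at every correlation examined, but it stays modest for weak associations. The result is therefore estimation, not a powered test. It also remains an association: every SLOW-BWL woman is assigned coaching and Contrave, so differences in adherence could drive both weight and outcome. The primary endpoint and its decision rule are untouched.

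**What to change.** Reword 4.2.1 and Section 13.2 before the secondary data are analysed:

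- **Analysis for the Section 3 hypothesis.** Fit the mixed model to all SLOW-BWL women, with a random effect for each woman, visit (baseline, 2 and 6 months) as a categorical term, and percentage weight change from baseline as a continuous term. Report the weight-change coefficient with its 95% confidence interval for each outcome. The visit terms absorb the average shift from time, coaching and drug.
- **Responder-only changes.** Keep them as descriptive summaries with intervals and state the number of women contributing.
- **Label.** Call the objective estimation and state that no power is claimed. If a power figure is wanted, give it for the weight-change coefficient over a range of assumed correlations.
- **Missing data.** Say how women without a 6-month weight enter this model. Section 13.4 counts them as non-responders for the primary endpoint, which does not supply a continuous weight change.

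The cost is a text amendment to two sections with the usual IRB approval. No new visits, samples or participants are needed.
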